PI: [name]

Date: 07Sep2022 Version: 2.0

The Effect of Inelastic Compression System on Quality of Life in People with Chronic Venous Insufficiency

IRB Number (eProst ID): 20210807

Protocol Version Number: 2.0

Protocol Version Date: 9/7/2022

PI Name: [name], MAS

NCT Number: NCT05051540

Page 1 of 12 Revised: June 17, 2020

PI: [name]

Date: 07Sep2022 Version: 2.0

1) Protocol Title

The Effect of Inelastic Compression System on Quality of Life in People with Chronic Venous Insufficiency

2) Objectives

The purpose of this protocol is to measure the effect of the use of an inelastic compression system (ICS) on quality of life (QOL) in patients with chronic venous insufficiency (CVI) who have demonstrated limited or no compliance with prescribed compression stockings or bandage wraps. The primary outcome of interest is the change in QOL of people who have CVI and use ICS over 6 weeks.

3) Background

Chronic venous insufficiency (CVI) is a common condition that affects about one third of adults in the US¹. The social and economic burden on both patients and society is significant; for instance, venous leg ulcers, a severe manifestation of CVI, costs the US healthcare system billions in dollars and the UK an amount of similar magnitude^{2,3}.

Notably, CVI negatively impacts patients' quality of life (QOL), particularly in those at advanced stages of disease⁴. This has been reported throughout various domains of well-being, including pain, physical functioning and mobility, and social isolation⁵. While generic scales like the 36-Item Short Form Survey (SF-36) are helpful to discern QOL measures across different disease groups, tools with specificity towards chronic venous diseases have been established^{6,7}. For instance, the Chronic Venous Insufficiency Questionnaire (CIVIQ-20) has been demonstrated to appropriately assess QOL in patients with CVI⁸ These tools may be used to guide clinical research practices in efforts to improve the well-being of these patients.

Several decades ago, the Clinical, Etiology, Anatomic, Pathophysiology (CEAP) classification was created to standardize the diverse manifestations of chronic venous insufficiency to allow for easier classification and communication of disease severity⁹. Specifically, within the Clinical portion of the CEAP system, the subcomponents C3-C5 refer to edema (C3), changes in skin and subcutaneous tissue (C4 -pigmentation, dermatitis, lipodermatosclerosis or atrophie blanche), and a healed ulcer (C5); these subcomponents increase numerically in proportion to the severity of the patient's condition¹⁰.

Currently, compression therapy is the first line treatment for all the manifestations of CVI ¹¹. However, existing compression hosiery are met with resistance by some patients. This results in a gap in compliance as for example up to 80% of patients who are prescribed compression stockings or bandaging wraps do not wear them as prescribed¹². This practice gap may contribute to the overall burden of CVI and solutions that address the need of patients who cannot wear compression stockings are needed. Inelastic compression wraps may help to solve this practice gap by offering easier application without compromising outcomes. One example of such a system is the Compreflex Compression Wrap system (Sigvaris Inc. Peachtree City, GA). This proposal is focused

Page 2 of 12

PI: [name]

Date: 07Sep2022 Version: 2.0

on determining if the usage of this specific inelastic compression wrap system in patients with CVI stages C3, C4, and C5 improves their quality of life.

4) Inclusion and Exclusion Criteria

Inclusion Criteria

- Subject is age 18 or older, able and willing to provide consent and agrees to comply with the study procedures
- Subject must have chronic venous insufficiency of stages C3, C4, or C5 according to the CEAP classification system
- Not compliant with their currently prescribed compression system

Exclusion Criteria

- Active malignancy other than non-melanoma skin cancer
- Study ulcer suspicious for cancer
- Unable to provide consent
- Subjects who are pregnant and/or breastfeeding
- In the opinion of the PI the subject cannot comply with study procedures

5) Study Design

- a) Primary Purpose: Treatment
- b) Interventional Study Model: Single Group
- c) Allocation: N/Ad) Enrollment: 40

This is a single center, single intervention, unblinded, prospective cohort study.

6)

7) Procedures Involved

This is a single center prospective cohort study that will last up to six 6 weeks per subject. A total of 30 patients will be enrolled, through the University of Miami Hospital and Clinics. The study is comprised of 3 visits per subject (see table 1) two in person and one over the phone. V0 will occur on the first day of the study. V1 will occur during the second week (between days 714) and the final visit, V2 on day 42 of the study.

At the enrollment visit (V0), subjects will undergo baseline assessments to determine eligibility for the study (inclusion and exclusion criteria, demographics, medical history, medication history, focused physical exam). Medical records will be reviewed for the subject's basic demographics, medical and surgical history, and current treatments. Once eligibility is confirmed, the patient will be assessed for measurements of disease severity (presence of varicose veins, atrophe

PI: [name]

Date: 07Sep2022 Version: 2.0

blanche, lipodermatosclerosis, hyperpigmentation, the Venous Clinical Severity Score VCSS (See Appendix A), itch severity using itch Numerical Rating Scale NRS (See Appendix B), pain using the Visual Analogue Scale VAS (See Appendix C), and limb circumference in mm.) Upon proper consent, photographs of the extremity will be captured and quality of life assessments will be completed. The two quality of life assessments used will be the Chronic Venous Disease Quality of Life Questionnaire (CIVIQ – 20) (See Appendix D), and the Short Form Healthy Survey (SF-36) (See Appendix E). The initial visit will conclude with proper product application training and time to address any questions.

Subjects will report for 2 successive follow-up visits. The first follow-up visit will be completed at least one week but no later than 14 days after the initial visit and be completed via phone (V1). During this visit, study staff will document concomitant medications, itch severity, pain, and assess patient adherence to usage of the inelastic compression system. If in the opinion of the study staff the subject is not able to apply the ICS effectively, they may convert the visit to video conferencing or even in person visit.

The third and final visit (V2) will be completed in person at the University of Miami Hospital Dermatology Clinical Trials Unit 6 weeks after the initial in person visit. During this visit, similar to the initial visit, study staff will document concomitant medications, perform a focused exam, measure disease severity and itch severity, and assess pain. Additionally, limb circumference measurements will be obtained and photographs of the extremity will be captured again. The visit will conclude with the same two quality of life assessments and assessment of adherence.

All subjects will continue to follow their care for all medical conditions as prescribed by their physician.

Visit	V0	V1 (phone)	V2
Day	0	7-14	42 (+/- 3)
Informed consent	X		
Eligibility	X		
Medical history	X		
Concomitant medications	X	X	X
Focused exam	X		X
Disease severity assessments	X		X
Itch severity	X	X	X
Pain assessment	X	X	X
Limb circumference	X		X
Photography	X		X
QOL assessment (CIVIQ-20, SF 36)	X		X
Product application training	X		
Adherence assessment		X	X

PI: [name]

Date: 07Sep2022 Version: 2.0

8) Study Endpoint

a) Primary Outcome Measure

- i) Title: Change in the Quality of Life
- ii) Description: As measured by the Chronic Venous Disease Quality of Life Questionnaire (CIVIQ-20) which is a questionnaire made up of 20 multiple choice questions subdivided into four categories: psychology, pain, physical repercussion and social repercussions. The questions are equally weighted and the value indicates the degree of deterioration of quality of life; 0 being the highest quality of life and 100 being the lowest. It has been tested to be a reliable measurement tool in evaluating the quality of life in those with CVI.
- iii) Timeframe: Baseline to 6 weeks

9) Data Banking

Physical study records will be in a locked cabinet in the Dermatology Clinical Trials Unit at University of Miami (University of Miami Hospital West Building, [name]). Technological study records will be located on a spreadsheet within a project file located within a password protected server on Microsoft Teams.

10) Data Management

The collected, deidentified data will be arrayed in a spreadsheet within a project file located within a password protected server on Microsoft Teams. Only the PI and approved study staff will have access to this file. Subject identities as participants in this study will be kept confidential for the remainder of the study and in any publication, and no identifiable patient information will be attributed to the dataset, thereby keeping them anonymous.

11) Risks to Subjects

The risks to the patient proposed by this trial are minimal as they do not pose greater potential for harm than routine clinical care. The potential risks are discussed below:

Potential Risks of the Inelastic Compression System

- Minor severity:
 - Skin Irritation or Discomfort
 - o Pain
- Major severity
 - Soft tissue injury

PI: [name]

Date: 07Sep2022 Version: 2.0

o Nerve Injury

These potential risks are unlikely. The risks listed under major severity have a lower likelihood of occurrence compared to the risks located under the minor severity category. Proper application of the inelastic compression system minimizes the probability of experiencing these potential risks.

12) Adverse Events and Serious Adverse Events

DEFINITION OF ADVERSE EVENTS (AE)

Adverse event means any untoward medical occurrence associated with the use of an intervention in humans, whether or not considered intervention-related (21 CFR 312.32 (a)). In the context of our study, an intervention refers to a study research procedure.

DEFINITION OF SERIOUS ADVERSE EVENTS (SAE)

A Serious Adverse Event (SAE) is any serious unfavorable and unintended sign, symptom, or disease temporally associated with this study protocol, whether or not considered related, including those that:

- o Results in death
- o Is life-threatening
- Requires inpatient hospitalization or causes prolongation of existing hospitalization
- o Results in persistent or significant disability/incapacity
- o Is a congenital anomaly/birth defect
- o Requires intervention to prevent permanent impairment or damage

Medical and scientific judgment should be exercised in determining whether an event is an important medical event. An important medical event may not be immediately lifethreatening and/or result in death or hospitalization. However, the important medical event should be reported as serious, if it is determined that the event may jeopardize the Participant and/or may require intervention to prevent one of the other adverse event outcomes.

CLASSIFICATION OF AN ADVERSE EVENT SEVERITY OF EVENT

The Investigator will provide an assessment of the severity of each adverse reaction by recording a severity rating on the appropriate SAE reporting page of the Participant's file. Severity, which is a description of the intensity of manifestation of the SAE, is distinct from seriousness, which implies a patient outcome or SAE-required treatment measure associated with a threat to life or functionality. Severity will be assessed according to the following scale. If required on the adverse event case report forms, the investigator will use the adjectives MILD, MODERATE, or SEVERE to describe the maximum intensity of the adverse event. For purposes of consistency, these intensity grades are defined as follows:

Page 6 of 12 Revised: June 17, 2020

PI: [name]

Date: 07Sep2022 Version: 2.0

MILD Does not interfere with Participant's usual

function.

MODERATE Interferes to some extent with Participant's

usual function.

SEVERE Interferes significantly with Participant's

usual function.

RELATIONSHIP TO STUDY INTERVENTION

For all collected AEs, the clinician who examines and evaluates the participant will determine the AE's causality based on temporal relationship and his/her clinical judgment. A binary assessment (related/not related) will be made and take into consideration the natural history of the underlying disease, concurrent illness, concomitant therapy, study-related procedures, accidents, and other external factors. While the relationship to the study tissue biopsy procedure (study research intervention) (related/not related) is part of the documentation process, it is not a factor in determining what is or is not reported in the study. All AEs are recorded regardless of relatedness. Related: The AE is known to occur with the study research procedure, there is a reasonable possibility that the study research procedure caused the AE, or there is a temporal relationship between the study agent and event. Reasonable possibility means that there is evidence to suggest a causal relationship between the study research procedure and the AE. An AE can be deemed related even if other factors may have contributed to the event.

Not Related: There is not a reasonable possibility that the study research procedure caused the event, there is no temporal relationship between the study research procedure and event onset, or an alternate etiology has been established or appears to provide a plausible explanation (e.g. the participant's clinical condition, underlying disease or concomitant treatments).

TIME PERIOD AND FREQUENCY FOR EVENT ASSESSMENT AND FOLLOW-UP At each visit, AEs/SAEs will be evaluated by the Investigator and recorded. All AEs must be recorded irrespective of whether they are considered study related. Information to be collected includes event description, time of onset, clinician's assessment of severity, relationship to study procedures, and time of resolution/stabilization of the event. All AEs occurring while on study must be documented appropriately regardless of relationship.

Any medical condition that is present at the time that the participant is screened will be considered as baseline and not reported as an AE.

Changes in the severity of an AE will be documented to allow an assessment of the duration of the event at each level of severity to be performed.

PI: [name]

Date: 07Sep2022 Version: 2.0

Any AEs/SAEs already documented at a previous assessment and designated as ongoing, should be reviewed at subsequent visits as necessary. If these have resolved, this should be documented.

ADVERSE EVENT REPORTING

All adverse events should be tracked from the time the Participant provides informed consent, and through the time of discharge from the study. Adverse events (serious and non-serious) should be recorded in the CRF for the duration of the reporting period. Adverse events reporting, including suspected serious unexpected adverse reactions, will be carried out in accordance with applicable local regulations.

All AEs that occur during the study will be recorded in the case report form and reported to IRB.

SERIOUS ADVERSE EVENT REPORTING

If a serious adverse event related to the study research procedures occurs, the IRB should be notified within 24 hours of awareness of the event by the investigator. In particular, if the serious adverse event is fatal or life-threatening, notification to IRB must be made immediately, irrespective of the extent of available adverse event information. This timeframe also applies to additional new information (follow-up) on previously forwarded serious adverse event reports.

In the rare event that the investigator does not become aware of the occurrence of a serious adverse event immediately (e.g., if an outpatient study Participant initially seeks treatment elsewhere), the investigator is to report the event within 24 hours after learning of it and document the time of his/her first awareness of the adverse event.

13) Potential Benefits to Subjects

A medical benefit cannot be guaranteed by this study. However, since study protocols mirror standard of care, subjects can reasonably expect to benefit medically (e.g. a decrease in lower extremity swelling or skin discoloration). Further, since the participation in the study is conditional of "failing" use of other standard care compressions devices, successful use of the ICS as part of this study, will be considered an improvement in medical care provided. Since study staff are part of the UM Wound Care Team, subjects will be cared for by expert wound care clinicians. Subjects' participation in this protocol will also help future patients with chronic venous insufficiency, as future patients may experience a high quality of life through usage of inelastic compression systems. Notably, medical care including dressings and medical advice are provided at no cost to subjects throughout the study period. Finally, as part of the informed consent subjects are reminded of alternative therapies that are available. It is our experience that subjects are very satisfied with the overall care in the UM clinical trials unit and often return

Page 8 of 12 Revised: June 17, 2020

PI: [name]

Date: 07Sep2022 Version: 2.0

for additional trials. Thus they are offered the psychological benefit of knowing that the UM clinical trials unit is always an option for them.

14) Setting

Study procedures will take place one of the following locations:

- [name] Department of Dermatology and Cutaneous Surgery

 Clinical Trials Unit. [name]
 [name].
- University of Miami Dermatology Outpatient Wound Care Clinic. [name]
- University of Miami Dermatology Outpatient Clinic. [name].

15) Resources Available

The University of Miami Wound Center is one of the largest and most advanced wound clinics in the United States, and together with its Hyperbaric Oxygen Unit attracts a large amount of patients with chronic wounds each week and venous disease. The investigators involved in this protocol are experienced clinicians with world-renowned expertise in wound healing and venous disease. Their staff consists of highly trained doctors, nurses and research fellows with extensive knowledge in the diagnosis and management of chronic wounds.

16) Recruitment Methods

Patients with chronic venous insufficiency seen for their routine care at the Dermatology or Wound Care outpatient clinics at the University of Miami Hospital will be identified for possible study eligibility by any of the dermatologists in our practice. If the treating dermatologist is a study team member, the patient will be asked if they are interested in being contacted by the study team to learn more about a protocol for chronic wounds. If interested, additional information will be provided and an informed consent form will be sent to the potential subject before scheduling a Screening Visit. A partial HIPAA waiver is needed, so that if the patient gives permission to be contacted by a member of the study team they will then be approached by a team member in clinic or will be contacted by phone if they consent. If the treating dermatologist is not a study team member, they will provide the potential subject with the contact information for the study team such that the patient can contact the study team for more information. If it is then determined that they are interested in participating, they will be scheduled for a visit at our Dermatology Clinical Trials Unit where informed consent and all other baseline visit study procedures will take place. The risks and benefits of the study will be presented, as well as the disclaimer that refusal to participate in the study will in no way, shape or form alter the type or quality of their care.

Page 9 of 12 Revised: June 17, 2020

PI: [name]

Date: 07Sep2022 Version: 2.0

Will Protected Health Information (PHI) be accessed prior to enrollment/consent? If so, please indicate "yes" below to request a Partial Waiver of HIPAA Authorization for Recruitment Purposes.

⊠Yes □No

17) Confidentiality

PHI will be collected from the EMR or subjects at UHealth. Data will be stored locally:

Other, specify: *PHI* will be stored in a binder inside a locked cabinet in the UMH Dermatology CTU. All PHI will be stripped of information that may be used to identify the subjects.

The research team will maintain the research data in compliance with applicable regulatory requirements and University of Miami data retention requirements as outlined in the Investigator Manual.

18) Provisions to Protect the Privacy Interests of Subjects

Throughout the duration of the entire study, the privacy interests of participants will be maintained by ensuring the presence of members approved to be involved in the study and maintaining absence of those who are not. Additionally, phone visits will be held in the UMH Dermatology CTU away from the public and personnel from other departments of the hospital.

19) Authorization for Use and Disclosure of Protected Health Information (HIPAA)

Confirm that you will destroy the Protected Health Information (PHI) you and/or your Study Team acquire receive from JHS and/or UHealth at the earliest opportunity.

☑ I confirm

Confirm that the Protected Health Inform (PHI) you acquire from JHS and/or UHealth will not be re-used or disclosed to any other person or entity, except as required by law or for authorized oversight of the research study or for other research for which the use or disclosure of PHI is permissible.

I Confirm

Notwithstanding the preceding "I confirm" statements above, I agree that neither I nor any member of the study team listed on the IRB submission for this Protocol shall ever

PI: [name]

Date: 07Sep2022 Version: 2.0

re-use or re-disclose any of the information acquired from Jackson Health System in any format, whether **identifiable or de-identified**, to any individual or entity without first obtaining written permission from Jackson Health System, even if such re-use or re-disclosure is permissible by law (e.g., HIPAA).

PI Signature	Date

20) Consent Process

Once patients are identified and consent to be contacted, they will be approached by a member of the study team during their outpatient visit OR will be contacted by a member of the study team by phone. Participants will be given ample time to consider their agreement. The study team will be available to answer any question in the method the participant prefers to communicate. No one in a perceived coercive position in relation to the participant will engage in the consenting process. Consent will be obtained voluntarily prior to initiating any study procedures.

Page 11 of 12 Revised: June 17, 2020

PI: [name]

Date: 07Sep2022 Version: 2.0

References:

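### The protocol gives two enrolment totals, 40 in Section 5(d) and 30 in Section 7, so the point at which recruitment stops is not fixed.

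*Protocol*

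**What the plan says.** Protocol Section 5 (Study Design), item d, gives the sample size as "Enrollment: 40". The same section describes the design: "This is a single center, single intervention, unblinded, prospective cohort study".

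Section 7 (Procedures Involved) gives a different total: "A total of 30 patients will be enrolled, through the University of Miami Hospital and Clinics".

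Section 8 (Study Endpoint) names one primary outcome, the change in CIVIQ-20, scored with "0 being the highest quality of life and 100 being the lowest", over "Timeframe: Baseline to 6 weeks".

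The protocol states no dropout rate, replacement rule, or separate target for patients who complete or are evaluable.

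**The concern.** Both sentences describe how many patients are enrolled, and they differ by 10. Neither sits in a change log. Because there is one centre and one group, 30 cannot be a site's or an arm's share of 40.

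Three things follow.

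- **The enrolment stop is undefined.** Stopping at 30 meets Section 7 and leaves Section 5 short. Going on to 40 meets Section 5 and exceeds Section 7. An IRB or auditor cannot tell from the protocol which would be a deviation.
- **The precision of the primary result depends on which sentence is followed.**
- **The text permits a data-dependent stop.** The study is unblinded, and under Section 10 the investigator and approved staff can open the data file. With two permitted end points, the choice between them could be made after seeing results. Nothing in the protocol suggests that this is planned, but a single number would rule it out.

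**Working it through.** **Inputs from the protocol.** Enrolment is 40 (Section 5(d)) and 30 (Section 7). The design is a single group. The primary outcome is a within-patient change in CIVIQ-20 on a 0 to 100 scale, from baseline to 6 weeks (Section 8).

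**Inputs assumed.** The protocol gives no significance level, power, effect size or SD. I use two-sided 5%, 80% power, and an SD of CIVIQ-20 change between 10 and 25 points, and I treat every enrolled patient as evaluable. Neither 40 nor 30 can be re-derived from the protocol, so the check covers whether the two can be reconciled and what the difference amounts to.

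**1. Can the totals be reconciled?** The gap is 40 − 30 = 10 patients, which is 25% of 40 and 33% of 30. If 30 were an evaluable target inflated for loss *d*, enrolment would be 30/(1 − *d*), rounded up:

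| Loss | Enrolment needed |
|---|---|
| 10% | 34 |
| 20% | 38 |
| 25% | 40 |

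Of the rates from 5% to 30% tried in steps of 5 points, only 25% reaches 40 exactly. The protocol states no such rate, and Section 7 says that the 30 are enrolled, not that they complete.

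**2. Precision.** The 95% half-width for a mean paired change, in units of the SD of change, is t(0.975, n − 1)/√n.

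- n = 30: 2.045/5.477 = 0.373
- n = 40: 2.023/6.325 = 0.320
- Ratio: 0.3734/0.3198 = 1.168, so the interval is about 17% wider at 30

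In CIVIQ-20 points:

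| Assumed SD of change | Half-width, n = 30 | Half-width, n = 40 |
|---|---|---|
| 10 | 3.7 | 3.2 |
| 15 | 5.6 | 4.8 |
| 20 | 7.5 | 6.4 |
| 25 | 9.3 | 8.0 |

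**3. Power (illustrative).** For a one-sample t test on the change, using the noncentral t distribution with n − 1 degrees of freedom and noncentrality (standardised change) × √n:

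| | n = 30 | n = 40 |
|---|---|---|
| Standardised change detectable with 80% power | 0.53 | 0.45 |
| Power if the true change is 0.45 SD | 66% | 79% |
| Power if the true change is 0.50 SD | 75% | 87% |

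**4. Worst case for the stopping point.** Suppose the change were tested at two-sided 5% after 30 patients and, only if not significant, tested again at the same level after 40. Simulation with no true change (400,000 replicates) gives an overall type I error of about 7.3% instead of 5%.

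**The case against.** The strongest reply accepts the mismatch but disputes how much rests on it.

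- **Justification may be in the SAP.** A sample-size rationale or precision statement may be in an analysis plan that is not shown. This stands, and I make no complaint that such a rationale is absent. It does not remove the conflict, because whichever number an SAP used, one of the two protocol sentences would still be wrong.
- **No optional stopping is described.** The protocol has no interim look, no test and no rule tied to results. This also stands. The 7.3% figure assumes deliberate use of both end points and a 5% test that the protocol does not state. It bounds what the text permits and says nothing about intent.
- **The power figures are conditional.** They are, and the 0.45 SD change is simply what 40 patients can detect with 80% power. The 17% difference in interval width needs fewer assumptions, but it still takes all enrolled patients as evaluable.
- **There may be a harmless explanation.** Section 7 determines eligibility at the enrolment visit, so an enrolled count could include people later found ineligible, and a 25% allowance links the figures exactly. One number may also just not have been updated. Either is plausible, but the protocol states neither.
- **The lack of a control group is a larger threat to a pre-post change than the choice between 30 and 40.** That is fair, but it is a separate matter and does not settle the enrolment total.

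**Conclusion.** The concern holds. Sections 5(d) and 7 state different enrolment totals for the same single-group study, and nothing in the protocol reconciles them. This should be corrected before the protocol is relied on, because the sample size is a core design figure and the two statements exclude each other.

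The effect on precision is moderate: an interval about 17% wider at 30 than at 40, assuming a t interval on paired changes with no losses. Figures in CIVIQ-20 points depend on the assumed SD, and the power figures on an assumed effect and a two-sided 5% level. The endpoint, its scale and its timing are unaffected. The documents do not show which total is correct, and I do not choose between them.

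**What to change.** State one enrolment number and use it in both Section 5(d) and Section 7. If 40 is the number enrolled and 30 the number expected to be evaluable, label each as such, state the 25% allowance (30/0.75 = 40), and say that recruitment stops when the enrolled count is reached, whatever the results to date. If an SAP or other study document quotes a sample size, bring it into line with the same figure.

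The cost is a short text amendment with no new procedures. If the number settled on is 30, the team should accept the wider interval, 0.373 rather than 0.320 SD of change.

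### Does scheduling a pain score at the phone visit, when the only pain scale named is a visual analogue scale, require a change to the protocol?

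*Protocol*

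**What the plan says.** All the relevant text on pain scoring is in section 7 (Procedures Involved) and its visit table.

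- **V0, in person.** Pain is measured with the VAS: "pain using the Visual Analogue Scale VAS (See Appendix C"). Itch is measured with a different type of scale: "itch severity using itch Numerical Rating Scale NRS (See Appendix B").
- **Visit pattern.** "The study is comprised of 3 visits per subject (see table 1) two in person and one over the phone".
- **V1, days 7-14.** The visit is to "be completed via phone (V1). During this visit, study staff will document concomitant medications, itch severity, pain". No instrument is named for pain here. If staff judge that the subject cannot apply the wrap effectively, "they may convert the visit to video conferencing or even in person visit".
- **V2, day 42, in person.** This visit is described as similar to the first. Staff "measure disease severity and itch severity, and assess pain", again without naming the scale.
- **Visit table.** The row "Pain assessment" is marked at V0, V1 and V2.

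Section 8 lists one endpoint, the change in CIVIQ-20 from baseline to 6 weeks. That questionnaire is "subdivided into four categories: psychology, pain, physical repercussion and social repercussions", so it has pain content of its own, but the visit table schedules it only at V0 and V2.

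**The concern.** A visual analogue scale is usually a line that the subject sees and marks. A phone call offers no line unless a form has been sent home, and the visible text mentions none. The natural guess is that staff would ask for a number aloud at V1 and set it against marks on a line at V0 and V2. A difference between V1 and either other visit would then mix a change in pain with a change in how pain was asked. Itch follows the same three-visit schedule but uses a numerical rating, which can be asked aloud, so pain looks like an oversight beside it.

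At stake would be the only scheduled pain score between baseline and week 6. This is also a matter of data collection: if scores were gathered in different ways and the mode was not noted, no later analysis could put that right.

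**Working it through.** The protocol gives no figure on this point, so there is none to reproduce. The check is a reading of the text and a count of what V1 touches.

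**Is a contradiction stated?** Two things must both be true for the concern to be a defect.

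1. *The VAS is the instrument at V1.* Section 7 names it only in the V0 paragraph. Carrying it forward to V1 is the natural reading, but the V1 paragraph says only that pain is documented.
2. *The VAS form cannot be used by phone.* Section 7 refers to Appendix C for the form. Appendices A to E are cited but are not in the text at hand. The form could be an unmarked line, a numbered line or a sheet taken home; the visible text does not say which.

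Neither can be confirmed. An appendix missing from the supplied text is not a gap in the plan.

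**How many scores are involved?** Inputs: three pain assessments per subject from the visit table, one of them at V1; enrollment of 40 in section 5 and 30 in section 7.

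- At 30 subjects: 30 × 3 = 90 scores, of which 30 × 1 = 30 are at V1.
- At 40 subjects: 40 × 3 = 120 scores, of which 40 × 1 = 40 are at V1.
- Either way the share is 1/3. It is an upper limit on the scores exposed, because a V1 visit converted to in person could use the same form as V0.

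**Which comparisons are involved?** Three visits give 3 × 2 / 2 = 3 pairs.

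| Pair | Involves V1 | Stated as an endpoint in the protocol |
|---|---|---|
| V0-V1 | yes | no |
| V1-V2 | yes | no |
| V0-V2 | no | no |

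Two of the three pairs could be affected. The V0-V2 pair, which spans the treatment period, has an in-person visit at both ends.

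**Which stated results are involved?** The CIVIQ-20 is given 0 times at V1, so 0 of 1 stated endpoints is affected. The protocol states no pain endpoint, no test of V1 pain and no decision that depends on the V1 score.

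**Is pain caused by the device lost at V1?** No. Section 12 has adverse events evaluated and recorded at each visit and graded as mild, moderate or severe. That route does not need the VAS.

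**What would a change of instrument cost?** A spoken rating at all three visits, with the VAS kept at V0 and V2, gives 3 + 2 = 5 pain items per subject against 3 now. That is 2 more per subject, or 60 more at 30 subjects and 80 more at 40. Replacing the VAS keeps the count at 3 but gives up comparability with reports that use a VAS. Neither choice fully removes the difference between phone and in-person answers.

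**The case for a change.** The strongest case for acting has three parts.

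*The fault lies in collection, so a SAP cannot repair it.* This is correct as a general point. If the mode at V1 is not noted, mode and change in pain cannot be separated afterwards. But how an item is asked on a call is ordinarily settled in a case report form or staff instruction, and nothing in the protocol prevents that.

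*Mode at V1 may be linked to pain.* Conversion to video or in person depends on poor application of the wrap. Section 11 lists pain as a device risk and says that proper application makes the listed risks less likely. Subjects seen in person at V1 could therefore differ in pain from those telephoned. The reasoning is sound, and it is a good reason for staff to note the mode. It would bias a V1 comparison only if one were made, and none is planned in the protocol.

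*V1 is the only post-baseline pain score for a subject who misses V2.* This is also true. The protocol gives no dropout rate, so the number of such subjects cannot be estimated. The point bears on a pain analysis that the protocol does not state, and leaves the primary outcome untouched.

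What stands is a caution: anyone who plots pain across all three visits should know how the V1 score was obtained before reading the middle point.

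**Conclusion.** No change to the protocol is needed. The text is silent on how pain is scored by phone; it does not contradict itself. The feared mismatch arises only if the VAS is meant at V1 and Appendix C offers no form usable by phone, and neither is shown. Staff can fill the gap sensibly in the ordinary working instructions.

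The size is small even if the mismatch is real. It would touch one of three pain scores per subject (30 of 90 or 40 of 120) and two of three possible comparisons, with no stated endpoint affected. No bias figure can be given, because the protocol has no data on the difference between modes. Changing the pain scale at all three visits would be a trade-off that alters no stated result.

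This conclusion rests on two assumptions: that V2 uses the same in-person scale as V0, as its description implies, and that no analysis planned elsewhere relies on the V1 pain score. The SAP, if there is one, was not available to confirm the second.
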